4.1.4 Drug assignment and administration of doses for each patient

The tracer dose (approximately 4mg in 20mL) of [⁸⁹Zr]Zr-BI 754111 will be injected intravenously via a pump in 10 min with flushing (10 mL physiologic saline). The mass dose might be adapted as per SMC decision. The injection will take place at the department of [REDACTED] Each patient will be administered [⁸⁹Zr]Zr-BI 754111 up to 2 times during the trial, once at Cycle1 no later than Day8 and at Cycle2 after the administration of BI 754091/BI 754111 treatment, if applicable (all patients in Part 1 and only patients tested positive for tumor LAG-3 expression in Part 2).

BI 754091 will be administered via intravenous infusion at the dose of 240mg. The first administration of BI 754091 treatment will take place at Cycle1 Day1 for each patient.

BI 754111 will be administered via intravenous infusion at the recommended expansion dose per trial 1381-0002. The first administration of BI 754111 treatment will take place at Cycle2 Day1 for each patient.

In Part 2, patients tested positive for tumor LAG-3 expression will be administered a lower or a higher dose of BI 754111 treatment at Cycle2 only. The dose allocated at these patients in Cycle2 will be confirmed by the SMC.

At Cycle2 and onwards, BI 754091 and BI 754111 treatment will be administered concomitantly.

For the preparation and administration of BI 754091 and BI 754111, please refer to the instruction provided in the ISF.

For each compound, the different timepoints of administration and the different doses are summarized in the table below.

Table 4.1.4: 1 Administration of doses per study part

Treatment Cycle	Study Part	Day	Dose to be administered
Cycle1 Baseline assessment	Part 1 and Part 2	C1 Day1	BI 754091 treatment: 240mg
		No later than day8	[⁸⁹ Zr]Zr-BI 754111: 4mg or adapted mass dose
Cycle2 On-treatment assessment	Part 1	C2 Day1	BI 754091 treatment: 240mg
			BI 754111 treatment: recommended exp. dose
	Part 2	C2 Day1	[⁸⁹ Zr]Zr-BI 754111: 4mg or adapted mass dose
			BI 754091 treatment: 240mg
			BI 754111 treatment: allocated dose per SMC decision
			[⁸⁹ Zr]Zr-BI 754111: 4mg or adapted mass dose
Cycle 3 and further cycles	Part 1 and Part 2	Cx Day1	BI 754091 treatment: 240mg
			BI 754111 treatment: recommended exp. dose

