	
• BI 754111: Recommended dose for the expansion phase of trial 1381-0002. Other doses, in the range of the doses tested in the dose escalation Part of trial 1381-0002, may be applied at Cycle2.• BI 754091: 240mg 
Doses administration at Cycle1 (baseline assessment phase):
 
• Cycle1 Day1: 1st administration of BI 754091• No later than day8: 1st administration of [⁸⁹Zr]Zr-BI 754111 
Doses administration at cycle 2 (on-treatment phase) and further cycles:
 
• Cycle 2 Day1: 1st administration of BI 754111 treatment in combination with BI 754091 followed by the 2nd administration of [⁸⁹Zr]Zr-BI 754111• In Part 2 during Cycle2, at least 2 different BI 754111 treatment doses in combination with BI 754091 will be assessed in patients tested positive for tumor LAG-3 expression• Cycle3 Day1 and further cycles: administration of the recommended expansion dose of BI 754111 treatment in combination with BI 754091
method and route of administration:	Intravenous infusion for BI 754111 and BI 754091 - once every 3 weeks Intravenous infusion for [⁸⁹ Zr]Zr-BI 754111 - once at Cycle1 and, if applicable, once at Cycle2
Duration of treatment:	Administration will continue until progression of disease (PD), unacceptable toxicity, or a maximum treatment duration of 1 year. If the patient is benefiting clinically at 1 year, he/she may continue on treatment after a case-by-case review with the sponsor
Statistical methods:	For both Parts of the study (Part 1 and Part 2) endpoints will be analysed by descriptive statistics. In Part 2, an exploratory analysis might be performed to model the association between BI 754111 treatment dose vs tumor uptake values (SUVs). These evaluations will be performed only if at least 3 different BI 754111 doses are investigated with a sufficient number of patients per dose (minimum of 3 patients per dose cohort). Association between tumor uptake and other imaging/efficacy or biomarker assessments will be investigated using generalized linear models. In addition, parameter-free correlation techniques, e.g. Kendall tau, will be provided where applicable. These analyses will be based on all data collected in the study.

Clinical Trial Protocol

Proprietary confidential information © 2020 Boehringer Ingelheim International GmbH or one or more of its affiliated companies

FLOW CHART

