4.1.2.2 BI 754111

BI 754111 treatment will be administered at doses expected to be therapeutically active based on non-clinical and clinical data.

The first dose to be investigated is the dose recommended for the expansion phase of trial 1381-0002. This dose was selected based on the data obtained in 1381-0002 dose-escalation cohorts, where 3 to 9 patients each received BI 754111 at dose levels of 4, 20, 80, 200, 400 and 600mg in combination with a flat dose of 240mg BI 754091. No DLTs or AESIs were observed in the dose escalation Part and maximum tolerated dose (MTD) was considered not reached.

The first administration of BI 754111 treatment will take place at Cycle2 Day1. In Part 2, various doses cohorts will be investigated sequentially. In each cohort, the dose applied at Cycle2 Day1 will depend on the magnitude of the blockade observed in the previous dose cohort. It is expected to explore at least two different dose levels of BI 754111 in this trial.

From Cycle3 Day1, the dose BI 754111 dose recommended for the expansion phase of trial 1381-0002 will be applied to all patients.

The treatment will be administered via infusion q3w.

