4.1.2.4 Dose modification for BI 754111 and BI 754091 treatments

There will be no dose reductions or escalations of BI 754091 or BI 754111 in any one patient. All patients (including patients allocated to a different dose of BI 754111 treatment during the on-treatment assessment phase (Cycle2) in Part 2), will take the recommended expansion phase dose of BI 754111 (determined in the 1381-0002 trial) starting from Cycle 3 onward.

The dose may be delayed for up to 6 weeks because of AEs, following discussion with the sponsor.

If treatment is held or discontinued due to an AE(s), both BI 754091 and BI 754111 will be held or discontinued together. If treatment is to be restarted after resolution (< Grade 1 or baseline) of the AE, both BI 754091 and BI 754111 must be started together.

The study treatments BI 754091 and BI 754111 should be permanently discontinued for CTCAE Version 5.0 Grade 3 or 4 pneumonitis, Grade 3 or 4 adrenal insufficiency, Grade 3 or 4 or recurrent colitis of any grade, Grade 4 diabetes mellitus, Grade 4 hypophysitis, Grade 4 rash, any grade encephalitis, any recurrent Grade 3 or 4 AE, transaminase values >5 times the ULN or total bilirubin >3 times ULN, inability to taper steroids to 10 mg or less prednisone or equivalent within 12 weeks, or persistent Grade 2 or 3 AEs that do not recover to Grade 1 or less within 12 weeks. Additional information of management of irAEs is provided in [Appendix 10.2](#).

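### Section 4.1.4 allows a Cycle 2 dose above the recommended expansion dose and gives no range, but on the listed levels no higher dose fits the synopsis limit.

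*Protocol*

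**What the plan says.** The protocol states the Cycle 2 dose of BI 754111 for LAG-3-positive Part 2 patients in several places.

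- **Synopsis, dose.** It gives the general dose first: "BI 754111: Recommended dose for the expansion phase of trial 1381-0002". It then adds: "Other doses, in the range of the doses tested in the dose escalation Part of trial 1381-0002, may be applied at Cycle2".
- **Section 4.1.4, text.** After naming the recommended expansion dose as the dose to be given, it says that LAG-3-positive patients in Part 2 "will be administered a lower or a higher dose of BI 754111 treatment at Cycle2 only". It continues: "The dose allocated at these patients in Cycle2 will be confirmed by the SMC".
- **Table 4.1.4: 1.** The Part 2 entry for Cycle 2 is "BI 754111 treatment: allocated dose per SMC decision".
- **Section 4.1.2.2.** It explains how the expansion dose was chosen, citing escalation cohorts "where 3 to 9 patients each received BI 754111 at dose levels of 4, 20, 80, 200, 400 and 600mg". For Part 2 it says that "the dose applied at Cycle2 Day1 will depend on the magnitude of the blockade observed in the previous dose cohort".
- **Section 4.1.2.4.** It mentions the Part 2 patients only in passing: "including patients allocated to a different dose of BI 754111 treatment during the on-treatment assessment phase (Cycle2) in Part 2".

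Only the synopsis ties the Cycle 2 dose to a tested range.

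**The concern.** Section 4.1.4 is where staff look for the dose to give. It is not merely silent about an upper limit: it names a dose above the recommended one as one of two options. If the recommended dose is already the top of the tested range, that option points outside the range the synopsis allows, and two parts of the same protocol disagree.

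What is at stake is a dosing rule, not an analysis. The protocol presents no safety data above 600 mg. Section 4.1.2.2 says that the maximum tolerated dose was considered not reached, so no such dose serves as an implied ceiling. A reader who relied on Section 4.1.4 alone would find permission to exceed the highest dose for which the protocol shows experience.

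**Working it through.** There is no sample size, power or error rate to reproduce. The check compares two dosing rules on the listed levels.

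**Inputs**

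- Listed escalation levels (Section 4.1.2.2): 4, 20, 80, 200, 400 and 600 mg.
- Expansion dose: 600 mg. No section states outright that the recommended dose is 600 mg. Section 1.4 reports 31 expansion patients treated at 600 mg, and SAP Section 6.1 gives 600 mg as the combination dose.
- Synopsis rule: another Cycle 2 dose *d* must lie between the lowest and highest tested levels.
- Section 4.1.4 rule: *d* is below or above the expansion dose, with no range.

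**Step 1. Synopsis rule.** 4 mg ≤ *d* ≤ 600 mg.

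**Step 2. Lower option.** *d* < 600 mg. Combined with step 1, this gives 4 mg ≤ *d* < 600 mg. Five listed levels qualify: 4, 20, 80, 200 and 400 mg.

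**Step 3. Higher option.** *d* > 600 mg. Combined with step 1, this needs *d* > 600 and *d* ≤ 600 together, which is impossible. No listed level qualifies.

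**Step 4. Dependence on the inferred expansion dose.** If it were 400 mg, one listed level (600 mg) would be a permitted higher dose. If it were 200 mg, two would be (400 and 600 mg). The clash in step 3 therefore depends on 600 mg being the expansion dose. The absence of a stated range in Section 4.1.4 does not.

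**Step 5. Does another section supply the limit?**

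- Section 4.1.2.2 lists the levels as the basis for choosing the expansion dose, not as a bound on Part 2. It also says that treatment doses are those expected to be therapeutically active, which is not a numeric cap.
- Section 3.2 says that the SMC confirms the dose with reference to the data available, again without a figure.
- Section 4.1.2.4 and Table 4.1.4: 1 give none.

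**Caveat on the list.** Six levels of at most 9 patients hold at most 6 × 9 = 54 patients, whereas Section 1.4 reports 55 treated at increasing doses. Different data cuts could explain this. It means only that the list may not be complete and current, so an unlisted level cannot be ruled out.

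**The case against.** The strongest reply is that there is no real contradiction. The synopsis is part of the protocol, so its limit applies whether or not Section 4.1.4 repeats it. The two options are alternatives, and any lower dose satisfies both texts. On this view the higher option is simply empty, and nobody is told to break the limit. That is right as far as it goes. A reader might infer that the protocol leaves the Cycle 2 dose uncapped; it does not. What remains is that Section 4.1.4 positively provides for a higher dose, which goes beyond silence and cannot be squared with the synopsis on the listed levels.

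The second reply is that controls exist. The SMC confirms each dose. Cohorts run in sequence and depend on the blockade already seen. Section 1.1 places Part 2 after blockade by a therapeutic dose has been confirmed, so lower doses are the more informative next step. This stands, and it is why the severity is low. SMC confirmation is nevertheless a procedure and not a numeric limit. The SMC plan cited in Section 8.7 was not available and may contain a cap. The Investigator's Brochure was not available either, so the absence of safety data above 600 mg from the protocol does not show that none exist.

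A reader might also infer that Section 4.1.4 wrongly denies these patients the recommended dose. The documents do not support that. Part 1 already tests that dose (Section 3.2), so moving to other doses in Part 2 is probably deliberate. The synopsis dose entry covers the whole trial and does not promise the recommended dose to this group at Cycle 2.

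**Conclusion.** The point holds as a low-severity inconsistency. On the levels in Section 4.1.2.2 and an expansion dose of 600 mg, none of the six listed levels is above the expansion dose, so the higher option in Section 4.1.4 is wrong as written. This rests on two assumptions: that 600 mg is the recommended expansion dose, and that no level above 600 mg was tested.

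No estimate is affected. SAP Section 7.4.1 summarises the primary endpoint descriptively by Cycle 2 dose cohort, whatever doses were used. SAP Section 4 records that the sponsor ended the study early, so the correction matters mainly if this protocol text is used again. The one-patient gap between 54 and 55 is a caveat about the level list. It should not be read as a second error or as evidence that a higher dose was given.

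**What to change.** In Section 4.1.4, replace the words offering a lower or higher dose with:

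> another dose within the range tested in the dose escalation part of trial 1381-0002 (maximum 600 mg on the levels listed in Section 4.1.2.2), as confirmed by the SMC

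Keep the restriction to Cycle 2. If a level above 600 mg was tested, state that level and its safety data in Section 4.1.2.2 and use that figure as the maximum.

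The cost is a change to one sentence, plus an addition to Section 4.1.2.2 if a higher level exists. The downside is that exceeding the tested range would need a protocol amendment, which the synopsis limit already implies.

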4.1.5 Blinding and procedures for unblinding

4.1.5.1 Blinding

In this open-label trial, treatment allocation will not be concealed throughout the trial. The CRF will contain information on allocated treatment.

4.1.5.2 Unblinding and breaking the code

Not applicable.

4.1.6 Packaging, labelling, and re-supply

The investigational products BI 754091 and BI 754111 will be provided by BI. [⁸⁹Zr]Zr-BI 754111 will be produced at the [REDACTED] campus, with a production license being in place. Production is performed under the responsibility of the hospital pharmacist (Qualified Person).

All products will be packaged and labelled in accordance with the principles of Good Manufacturing Practice (GMP). Re-supply to the site will be managed by BI in collaboration with the investigational site, which will also monitor expiry dates of supplies available at the site.

For details of packaging and the description of the label, refer to the ISF.

4.1.7 Storage conditions

BI 754091 and BI 754111 will be kept in their original packaging and in a secure limited access storage area according to the recommended storage conditions on the medication label. A temperature log must be maintained for documentation.

Proprietary confidential information © 2020 Boehringer Ingelheim International GmbH or one or more of its affiliated companies

If the storage conditions are found to be outside the specified range, the BI clinical monitor (as provided in the list of contacts) must be contacted immediately.

[⁸⁹Zr]Zr-BI 754111 should be stored at 2-8°C until use. Prior to drawing up in a syringe it should be warmed up to room temperature. It can be kept in a syringe for approximately 1 hour.

4.1.8 Drug accountability

The investigator or pharmacist/ investigational drug storage manager will receive the investigational treatment drugs delivered by the sponsor when the following requirements are fulfilled:

- Approval of the clinical trial protocol (CTP) by the institutional review board (IRB)/ethics committee (EC)
- Availability of a signed and dated clinical trial contract between the sponsor and the investigational site
- Approval/notification of the regulatory authority, e.g. competent authority
- Availability of the curriculum vitae of the Principal Investigator
- Availability of a signed and dated clinical trial protocol
- Availability of the proof of a medical license for the Principal Investigator

Investigational drugs are not allowed to be used outside the context of this protocol. They must not be forwarded to other investigators or clinics.

The investigator or pharmacist/ investigational drug storage manager must maintain records of the product's delivery to the trial site, the inventory at the site, the use by each patient, and the return to the sponsor or warehouse/drug distribution centre or alternative disposal of unused products. If applicable, the sponsor or warehouse/drug distribution centre will maintain records of the disposal.

These records will include dates, quantities, batch/serial numbers, expiry ('use- by') dates, and the unique code numbers assigned to the investigational product and trial patients. The investigator/pharmacist/ investigational drug storage manager will maintain records that document adequately that the patients were provided the doses specified by the CTP and reconcile all investigational products received from the sponsor. Unused and Partially used trial drugs will be destroyed on site at the end of the trial (after relevant reconciliations have been completed and records reviewed by the clinical monitor).

4.2 OTHER TREATMENTS, EMERGENCY PROCEDURES, RESTRICTIONS

4.2.1 Other treatments and emergency procedures

There are no other mandatory treatments to be used or special emergency procedures to be followed in this trial.

Rescue medications to reverse the action of BI 754111 or BI 754091 are not available. Therefore, potential side effects of the study drugs have to be treated symptomatically.

Proprietary confidential information © 2020 Boehringer Ingelheim International GmbH or one or more of its affiliated companies

Concomitant therapy, with reasons for taking each treatment, must be recorded in the eCRF during the screening and treatment periods, starting at the date of signature of the ICF and ending at the 30-day follow-up visit. After the 30-day follow up, only concomitant therapy indicated for treatment of a related AE has to be reported. If a new anti-cancer treatment is started, it will be documented in the eCRF.

Permitted concomitant medications include:

- If medically feasible, patients taking regular medication should be maintained on it throughout the trial.
- *To reduce the risk of IRRs, patients are to be pre-treated with an antihistamine and acetaminophen or paracetamol. Pre-treatment should be administered at sufficient time prior to initiation of infusion to allow the agents to exert their effect.* Supportive care and other medications that are considered necessary for the patient's well-being may be given at the discretion of the Investigator.
- Blood transfusions are allowed at any time during the trial, except to meet eligibility criteria.
- Patients already receiving erythropoietin at the time of screening for the trial may continue it, provided they have been receiving it for more than one month at the time trial treatment is started. Prophylactic erythropoietin should not be started during the first 3 weeks of any cohort, but may be started thereafter.
- Granulocyte colony stimulating factors should not be used prophylactically during the first 3 weeks of any cohort. Thereafter, prophylactic colony stimulating factors may be used according to institutional standards.
- For symptom control, palliative radiotherapy is permitted during the trial, except during the biodistribution imaging phases as it could interfere with the imaging evaluation. Palliative radiotherapy is allowed provided that the reason for radiotherapy does not reflect PD and does not interfere with response assessment. Lesions that have been exposed to radiotherapy are no longer evaluable, and may not be included in the assessment of the non-target lesions and the overall assessment. Unless in emergency situations, the BI Medical Monitor should be contacted prior to the administration of palliative radiotherapy.

4.2.2 Restrictions

4.2.2.1 Restrictions regarding concomitant treatment

- No other investigational therapy or anticancer agent should be given to patients. If such agents are required for a patient, then the patient must first be withdrawn from the trial.
- Immunosuppressive medications including, but not limited to systemic corticosteroids at doses exceeding 10 mg/day of prednisone or equivalent, methotrexate, azathioprine, and tumor necrosis factor-alpha blockers are prohibited. Use of immunosuppressive medications for the management of investigational product-related AEs or in patients with contrast allergies is acceptable, and does not necessarily warrant immediate treatment discontinuation. In addition, use of inhaled, topical, intranasal corticosteroids or local steroid injections (e.g., intra-articular injection) is permitted. Temporary uses of corticosteroids for concurrent illnesses (e.g., food allergies, computed tomography (CT) scan contrast hypersensitivity) are acceptable upon discussion with the Medical Monitor.

Proprietary confidential information © 2020 Boehringer Ingelheim International GmbH or one or more of its affiliated companies

- Live attenuated vaccines are prohibited during the trial through 30 days after the last dose of investigational product.
- Herbal preparations/medications are not allowed throughout the trial unless agreed to by the Principal Investigator. These herbal medications include, but are not limited to: St. John's wort, kava, ephedra (ma huang), gingko biloba, dehydroepiandrosterone (DHEA), yohimbe, saw palmetto, and ginseng. If instructed by the Principal Investigator, patients should stop using these herbal medications 7 days prior to first dose of study treatment.

4.2.2.2 Restrictions on diet and life style

The usual restrictions on diet and life style that were already applicable for a given patient before entry into the trial, according to his/her medical condition, have to be continued.

4.2.2.3 Contraception requirements

Due to the advanced stage of disease of Phase I trial patient populations and the high medical need, WOCBP (for the definition please refer to [Section 3.3.2](#)) can be included in this trial provided that they agree to use a highly-effective contraception method.

WOCBP and men able to father a child must use highly effective methods of birth control per the ICH M3 (R2) that result in a low failure rate of less than 1% per year when used consistently and correctly.

WOCBP and men able to father a child must use two medically approved methods of birth control throughout the trial, and for a period of at least 6 months after last trial drug intake. They must use one barrier method, i.e. condom or occlusive cap with spermicide, or vasectomized Partner, and one highly effective non-barrier method including oral, injected or implanted hormonal contraceptives, intrauterine device or system.

Male patients: men whose Partner is a WOCBP must use condoms and ensure their Partner is using an additional highly-effective method of birth control, during the trial and until at least 6 months after the end of the trial treatment.

Female patients: WOCBP must use highly-effective methods of birth control per ICH M3 (R2) that results in a low failure rate of less than 1% per year when used consistently and correctly during the study, and for a period of at least 3 months after the last dose of study drug.

Acceptable methods of birth control for this trial are:

- Combined (estrogen and progestogen containing) hormonal birth control that prevents ovulation (oral, intravaginal, transdermal).
- Progestogen-only hormonal birth control that prevents ovulation (oral, injectable, implantable).
- Intrauterine device (IUD) or intrauterine hormone-releasing system (IUS).
- Bilateral tubal occlusion
- Vasectomised sexual Partner with documented absence of sperm.

Or

Proprietary confidential information © 2020 Boehringer Ingelheim International GmbH or one or more of its affiliated companies

- Patients must abstain from male-female sex. This is defined as being in line with the preferred and usual lifestyle of the patient. Periodic abstinence e.g. calendar, ovulation, symptothermal, post-ovulation methods; declaration of abstinence for the duration of exposure to study drug; and withdrawal are not acceptable.

Details of these contraception methods are described in the patient information in the ICF.

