3.3.2 Inclusion criteria

For inclusion in the trial, patients must fulfil all of the following criteria:

1. Provision of signed and dated, written Informed Consent Form (ICF) prior to any trial-specific procedures, sampling, or analyses
2. Patients of legal age (according to local legislation) at the time of signature of the ICF
3. Patients with histologically confirmed diagnosis of recurrent NSCLC who received anti-PD-1 or anti-PD-L1 as Part of last treatment with at least 3 months of stable disease (i.e. patients with confirmed response (PR or CR) regardless of duration of response or stable disease (SD) for a minimum of 3 months) and have become refractory to anti-PD-1/ anti-PD-L1 based treatment
OR
Patients with histologically confirmed diagnosis of recurrent metastatic HNSCC who progressed after platinum based therapy or not indicated for receiving standard (radio) chemotherapy (previous treatment with anti- PD-1/ PD-L1 is allowed)
4. Eastern Cooperative Oncology Group (ECOG, [R01-0787](#)) score: 0 to 1
5. Patient must have at least one PET imageable and evaluable tumor lesion of 20mm
6. Patients must have at least one tumor lesion amenable to biopsy. This lesion should be PET imageable and evaluable as defined above and the biopsy should be obtained before first BI 754091 administration, unless medically contra-indicated. In the latter case, 25 4µm sections from an archival biopsy taken at relapse after the previous treatment are acceptable
7. Must have evaluable lesion(s) according to Revised Response Evaluation Criteria in Solid Tumors (RECIST) Version 1.1 and iRECIST

Proprietary confidential information © 2020 Boehringer Ingelheim International GmbH or one or more of its affiliated companies

8. Life expectancy of at least 12 weeks after the start of the treatment according to the Investigator's judgement
9. Male or female patients. Women of childbearing potential (WOCBP)¹ and men able to father a child must be ready and able to use highly effective methods of birth control per International Conference on Harmonisation (ICH) M3 (R2) (that result in a low failure rate of less than 1% per year when used consistently and correctly) during trial Participation and for at least 6 months after the last administration of trial medication. A list of contraception methods meeting these criteria is provided in the patient information.

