5.2.6.2.4 Pregnancy

In rare cases, pregnancy might occur in a clinical trial. Once a patient has been enrolled in the clinical trial and has taken trial medication, the investigator must report any drug exposure during pregnancy in a trial Participant immediately (within 24 hours) by means of Part A of the Pregnancy Monitoring Form to the sponsor's unique entry point.

The outcome of the pregnancy associated with the drug exposure during pregnancy must be followed up and reported to the sponsor's unique entry point on the Pregnancy Monitoring Form for Clinical Trials (Part B).

The ISF will contain the Pregnancy Monitoring Form for Clinical Trials (Part A and B).

As pregnancy itself is not to be reported as an AE, in the absence of an accompanying SAE and/or AESI, only the Pregnancy Monitoring Form for Clinical Trials and not the SAE form is to be completed. If there is an SAE and/or AESI associated with the pregnancy an SAE form must be completed in addition.

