4. CHANGES IN THE PLANNED ANALYSIS OF THE STUDY

This is the initial version of TSAP and there is no change in the analysis plan since the finalization of the protocol version 3.0.

The study was prematurely terminated by the sponsor.

Other than specified in the CTP, the following analyses will not be performed by BI:

[REDACTED]

[REDACTED]

[REDACTED]

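### Protocol 4.2.2.3 gives women of childbearing potential two different minimum contraception periods after the last dose: 3 months in the female paragraph, 6 months in the general paragraph and in inclusion criterion 9

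*Protocol*

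**What the plan says.** Three sentences in the protocol set a post-treatment contraception period for women of childbearing potential (WOCBP).

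- **3.3.2, inclusion criterion 9**, addressed to WOCBP and to men able to father a child: highly effective birth control "during trial Participation and for at least 6 months after the last administration of trial medication".
- **4.2.2.3, general paragraph**, addressed to the same two groups: two approved methods of birth control "throughout the trial, and for a period of at least 6 months after last trial drug intake".
- **4.2.2.3, 'Female patients' paragraph**, addressed to WOCBP: highly effective methods during the study "and for a period of at least 3 months after the last dose of study drug".

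The 'Male patients' paragraph of 4.2.2.3 asks for condoms plus an additional highly effective method used by the partner, "during the trial and until at least 6 months after the end of the trial treatment". On what patients are told, the section adds: "Details of these contraception methods are described in the patient information in the ICF". The patient information itself is not in the reviewed copy.

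**The concern.** A woman must accept at least 6 months of contraception after treatment to enter the trial, yet the paragraph written specifically for women asks for only 3. That paragraph is where staff advising a female patient would naturally look. Someone relying on it alone could advise her that contraception may end 3 months before the period she agreed to at entry.

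The protocol has little else in place for those months. By the Flow Chart, the last scheduled pregnancy test is at the end-of-treatment visit, and none is planned at the 30-day follow-up. After the patient's end of trial, 5.2.6.2.1 no longer asks the investigator to monitor actively for adverse events. Section 5.2.6.2.4 requires drug exposure during pregnancy to be reported within 24 hours and the outcome followed up, but that applies only once a pregnancy has occurred.

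**Working it through.** No calculation beyond a subtraction applies. The check is to set the sentences side by side and ask whether anything reconciles them.

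| Place | Who | Methods | Minimum period after treatment |
|---|---|---|---|
| 3.3.2, criterion 9 | WOCBP; men able to father a child | Highly effective, ICH M3 (R2), failure rate below 1% per year | 6 months |
| 4.2.2.3, general paragraph | WOCBP; men able to father a child | Two methods: one barrier, one highly effective non-barrier | 6 months |
| 4.2.2.3, female paragraph | WOCBP | Highly effective, ICH M3 (R2), failure rate below 1% per year | 3 months |
| 4.2.2.3, male paragraph (comparison) | Men with a WOCBP partner | Condom plus the partner's highly effective method | 6 months |

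Difference for women: 6 − 3 = 3 months. Of the three sentences that apply to women, two say 6 months and one says 3.

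**Different population?** No. All three sentences cover WOCBP enrolled in the trial.

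**Different starting point?** No. All three run from the last dose or administration.

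**Different methods?** The general paragraph could be read as attaching 6 months only to the two-method rule, leaving 3 months for a single highly effective method. Criterion 9 rules that out, because it attaches 6 months to the same standard that the female paragraph names.

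**A later, deliberate change?** Nothing in Section 11 suggests it. Global Amendment 1 lists 4 changed sections and Global Amendment 2 lists 16; neither names 3.3.2 or 4.2.2.3, although the second does name 4.2.1. One item of the second list is redacted, but it stands between 1.4 and 3.1 in a list kept in section order.

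**Lower exposure in women?** The male paragraph points the other way. The undosed partner of a male patient is to be covered for at least 6 months after treatment ends. Read alone, the female paragraph gives a woman who received the drugs half that time, and no reason is offered.

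**The case against.** The strongest reply is that the sentences can all be obeyed at once. Each period is a minimum, none tells a woman to stop at 3 months, and 6 months satisfies all of them. The 6-month rule stands slightly earlier in the same section and is also an entry criterion. The trial runs at a single specialised centre, so different readings across sites do not arise. Scheduled contact ends with the visit 30 (+2) days after the end-of-treatment visit, so there is no visit at month 3 at which a woman would be told to stop. What women were told depends largely on the unseen patient information. The SAP (Section 4) records: "The study was prematurely terminated by the sponsor". The amendment lists also cannot show whether 3 months was an error or a choice in the original text.

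These points are fair and they limit the practical effect. Harm is possible but not shown, and there may be no woman to whom a correction still matters. They do not remove the mismatch: two minimums for the same women, from the same starting point and for the same class of methods, cannot both be the intended rule. That 6 months satisfies every sentence tells the reader which figure is safe to adopt; it does not make the 3-month sentence correct.

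**Conclusion.** The concern holds. The female paragraph of 4.2.2.3 understates, by 3 months, the period that criterion 9 and the general paragraph require of the same women. Confidence is high for the textual conflict, which stands in current protocol text with no redaction in the sentences concerned.

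No consequence has been demonstrated. The number of WOCBP enrolled is not given, and nothing in the documents shows that 3 months is too short pharmacologically. Preferring 6 months rests on its being the entry requirement and the only stated figure that meets every sentence. This is an inconsistency in a patient-safety rule that should be corrected; it has no bearing on endpoints, sample size or analyses.

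**What to change.** In the 'Female patients' paragraph of 4.2.2.3, change the period after the last dose from 3 to 6 months. Check that the patient information gives 6 months, and correct it if it does not.

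Because the study ended early, a one-paragraph clarification to the site is enough, and it is needed only if any woman is still within 6 months of her last dose. No last-dose dates are given in the documents, so the sponsor would have to check; there may be none.

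The cost is one figure in the protocol, or the short clarification, plus the check of the patient information.
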